#### 9.4.2 ANALYSIS OF THE SECONDARY ENDPOINT(S)

The Microsoft Excel file will have all participant appointment attendance records and responses to schedule text-messages, which were downloaded to determine acceptability as: 1) > 90% adherence to the BAT and CBT session schedule; 2) responsiveness to text-messages as: a) >80% of all two-way messages replied to during the set of blocked hours; b) >90% of participants reporting direct benefit from one-way text messages; 3) positive responses coded from post-intervention exit interview transcripts (to be determined at future date); 4) limited number of barriers to participation reported (to be determined at a future date).

#### 9.4.3 SAFETY ANALYSES

This section is not applicable for behavioral clinical trials.

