### 1.2 SCHEMA

***Flow Diagram - See Attached Figure of Sequential Multiple Assignment Randomized Trial Design.***

## 1.3 SCHEDULE OF ACTIVITIES

	Pre-screening (Pre-consent)	Visit 1 Day 1	Visit 2 Day 7	Visit 3 Day 14 ±7	Visit 4 Day 21 ±7	Visit 5 Day 28 ±7	Visit 6 Day 35 ±7	Visit 7 Day 42 ±7	Visit 8 Day 49 ±7	Visit 9 Day 56 ±7	Visit 10 Day 63 ±7	Visit 11 Day 70 ±7	Final Visit Day 84 ±7
Screen for Eligibility	X												
Informed Consent		X											
Demographics		X											
Depression and Text-Message Criteria		X					X						
Outcome Evaluation													
Depression Ratings		X	X	X	X	X	X	X	X	X	X	X	X
Randomization		X		X									
1 st Stage Intervention		X	X	X	**	X*	X* 						
Primary Tailoring Variable - Decision Point on Sequencing				X									
2 nd Stage Intervention					X	X	X*	X*	X*	X*	X*	X*	
Adverse Events Reporting			X	X	X	X	X	X	X	X	X	X	X

\*Participants will all start with the first stage treatment - This is BAT with or without text-messaging support. After 3 of 5 sessions - approximately half-way through the intervention - their depression ratings are assessed that specifically inform the next course - This is called the second-stage treatment. Participants may either continue to complete the 5 sessions their first-stage treatment (i.e., BAT), get one extra booster session (denoted by \*1), or switch to CBT, which includes up to 11 sessions (denoted by \*).

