## 2.3 RISK/BENEFIT ASSESSMENT

### 2.3.1 KNOWN POTENTIAL RISKS

1. Breaches of confidentiality.
2. Inconvenience to the participant.
3. Intervention does not relieve depression symptoms in participant.
4. Mood changes - Participant experiences greater depressive symptoms during the course of the study.

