## 8.2 SAFETY ASSESSMENTS

Not applicable as this intervention does not involve any medical or pharmacological components that would warrant a physical safety assessment.

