#### 8.3.4 TIME PERIOD AND FREQUENCY FOR EVENT ASSESSMENT AND FOLLOW-UP

The occurrence of an AE or serious AE (SAE) may come to the attention of study personnel during study visits and interviews of a study participant presenting for medical care, or upon review during team meetings.

All AEs, not otherwise precluded per the protocol, will be captured following the Reporting Requirements Summary Sheet from the UCSF IRB (Attached in the IRB application). Information to be collected includes event description, time of onset, clinician's assessment of severity, relationship to study procedures (assessed only by those with the training and authority to make a diagnosis), and time of resolution/stabilization of the event. All AEs occurring while on study will be documented appropriately regardless of relationship. All AEs will be followed to adequate resolution.

Any medical or psychiatric condition that is present at the time that the participant is screened will be considered as baseline and not reported as an AE. However, if the study participant's condition deteriorates at any time during the study, it will be recorded as an AE.

Changes in the severity of an AE will be documented to allow an assessment of the duration of the event at each level of severity to be performed. Documentation of onset and duration of each episode will be maintained for AEs characterized as intermittent.

The interventionist will record events with start dates occurring any time after informed consent is obtained. At each study visit, the interventionist will inquire about the occurrence of AE/SAEs since the last visit. Events will be followed for outcome information until resolution or stabilization. This is determined during weekly team meetings for AEs, and immediate scheduling of meetings for SAEs.

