#### 10.1.7 CLINICAL MONITORING

Clinical monitoring refers to independent monitoring plans. An agreement will be made with the PI and Drs. [name] and [name] (Clinic Director and Medical Director) to immediately report any detection of significant distress and breaches of confidentiality given that the study will take place at the Salud Clinic at ZSFGH. Should any breach of confidentiality or adverse events occur, the PI will convene an ad hoc meeting with Drs. [name] (faculty mentor) and [name] (internal medical monitor) to review options to stop the study, recommend removing the participant from the study, or change any intervention procedures to eliminate any potential risks that are occur at unacceptable levels.

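### Section 9.4.3 rules out any safety analysis because the trial is behavioural, so the adverse events the protocol collects have no planned summary, and worsening depression is not defined or counted as a harm

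*Combined protocol and SAP*

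**What the plan says.** Protocol Section 9.4.3 (Safety Analyses) consists of one sentence: "This section is not applicable for behavioral clinical trials". The SAP has a statement of aim, a primary-endpoint section and a secondary-endpoint section. It does not mention safety.

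Elsewhere the protocol sets up detailed collection of harm data:

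- Section 2.3.1 lists as a known risk: "Participant experiences greater depressive symptoms during the course of the study".
- Section 1.3 has a row headed "Adverse Events Reporting", marked at Visits 2 to 11 and at the Final Visit.
- Section 8.3.4 states: "At each study visit, the interventionist will inquire about the occurrence of AE/SAEs since the last visit". On content it says: "Information to be collected includes event description, time of onset, clinician's assessment of severity, relationship to study procedures", together with the time of resolution. On scope it says: "All AEs occurring while on study will be documented appropriately regardless of relationship". It also has a condition present at screening recorded as an AE if it deteriorates during the study.
- Sections 8.3.3.1 to 8.3.3.3 define severity, relatedness and expectedness.

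Section 8.2 (Safety Assessments) reads: "Not applicable as this intervention does not involve any medical or pharmacological components that would warrant a physical safety assessment".

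Sections 9.4.1 and 9.4.7 and the SAP's primary-endpoint section provide for tables of depression ratings from baseline through follow-up. Section 9.4.7 specifies these for each participant and in aggregate.

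**The concern.** The reason given in 9.4.3 is the type of trial, but the harm the protocol itself names is psychological and is one a behavioural trial can measure. The section is a stated decision to have no safety analysis, and it sits badly with the effort spent on collecting and grading events.

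Three parts of the protocol also depend on how often events happen:

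- Sections 8.3.3.3 and 8.3.5 judge whether an event is unexpected partly by its frequency.
- Section 10.1.2 lists unacceptable risk among the grounds for suspending or ending the study.
- Section 3 defines acceptability partly as tolerability.

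Followed as written, the pilot could report its feasibility and acceptability results with no planned statement of how many participants had an AE, a related AE or an SAE, overall or by starting arm. The full-scale SMART that this pilot is meant to inform would then be designed without that summary.

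**Working it through.** The plan gives no safety figure to reproduce. The check is a comparison of sections, followed by the precision that a safety table would have.

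**Step 1. What is collected.** The Section 1.3 schedule has 12 study visits (Visits 1 to 11 and the Final Visit), and the AE row is marked at 11 of them. Visit 1 is blank there, although 8.3.4 records events from consent onward. With 45 participants (Section 9.2) that is up to 45 × 11 = 495 scheduled AE enquiries.

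**Step 2. What is done with it.**

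| Place | Use of harm data |
|---|---|
| 8.3.5, 8.3.6 | Individual reports to the IRB, only if related and also serious or unexpected |
| 8.3.4, 10.1.6, 10.1.7 | Discussion at team, mentor, ad hoc and quarterly meetings |
| 9.4.1, 9.4.7, SAP primary section | Tables of depression ratings; no definition or count of worsening |
| 9.4.3 | Declared not applicable |
| SAP, all sections | No AE or SAE count, rate, listing or comparison by arm |

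No row is a planned summary of AEs or SAEs.

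**Step 3. Precision of a table.** With no events in n participants, the exact two-sided 95% upper limit is 1 − 0.025^(1/n).

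- All participants, n = 45: 1 − 0.025^(1/45) = 7.9%. The one-sided 95% limit is 1 − 0.05^(1/45) = 6.4%.
- One first-stage arm, n about 22 (half of 45): 1 − 0.025^(1/22) = 15.4%.
- An outcome group at the Section 9.2 minimum, n = 4: 1 − 0.025^(1/4) = 60.2%.

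Intervals are therefore useful overall, weak but still readable by first-stage arm, and nearly empty by outcome group.

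**Step 4. Would there be anything to report?** The documents give no AE rate, so a range is assumed. The chance of at least one affected participant among 45 is 1 − (1 − p)^45:

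| Assumed true risk p | Chance of at least one in 45 |
|---|---|
| 2% | 60% |
| 5% | 90% |
| 10% | 99% |

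**Step 5. How worsening should be counted.** One option is to count anyone rated above baseline at any visit. Section 1.3 schedules 12 depression ratings per participant. Assume no true change, exchangeable ratings and no ties. Baseline is then the highest of the 12 with probability 1/12, so 1 − 1/12 = 92% would be labelled worse at some visit. Real ratings have ties and trends, so 92% is illustrative, but a count with no margin over many visits would mostly measure noise. Fixed time points and a margin set in advance are needed.

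**The case against.** The best defence is that AE recording here serves IRB reporting and case-by-case oversight. That can coexist with no statistical safety analysis in a 45-person pilot that states no hypotheses (Section 9.1). Events are reviewed at weekly meetings, SAEs prompt immediate meetings, and because every AE is recorded in detail a table could be made later. Section 8.2 limits its exemption to physical assessments, so it does not contradict the mood risk. Much of this stands: oversight does not wait for 9.4.3, and no feasibility or acceptability criterion in Section 9.4 changes. It does not justify 9.4.3, however. The trial is already wholly descriptive, and a descriptive AE table needs no hypothesis.

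A reader might infer more than the documents support:

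- *That all harm data go unsummarised, or that the trial could not say who worsened.* The depression ratings are to be tabulated per participant and in aggregate, so worsening can be read from them. The gap there is only the definition and the count.
- *That the monitors have no event rate to judge.* Sections 7.1 and 8.3.7 refer to a data and safety monitoring plan that is not included. It may provide summaries, and this cannot be checked.
- *That the quarterly meeting is charged with changing procedures* "to eliminate any potential risks that are occur at unacceptable levels". Those words are in Section 10.1.7, about an ad hoc meeting called after an adverse event or a breach of confidentiality. The quarterly meeting is in 10.1.6, which gives no such criterion.
- *That the PHQ-9 is taken at every visit.* The schedule says only that depression is rated. The PHQ-9 is named for eligibility and for the response decision, and 8.1 says the same rating is used at the end.

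**Conclusion.** The point holds in a limited form. Section 9.4.3 excludes safety analysis for a reason that the rest of the protocol does not bear out, and neither Section 9 nor the SAP plans any summary of AEs or SAEs. Worsening depression, a listed risk, will be visible in planned tables but is not defined or counted as a harm.

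The consequence is a reporting gap. It does not affect the sample size or the feasibility and acceptability criteria, and nothing here shows that participant oversight fails. The information at stake is modest but real: with no events in 45, a true risk above 7.9% lies outside the exact two-sided 95% interval. This assumes that all 45 are enrolled and contribute AE data; with 40 the limit is 8.8%. It also assumes that the unseen monitoring plan, whatever it contains, does not replace a safety section in the SAP. The change should be made before analysis.

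**What to change.** Replace Section 9.4.3 and add a matching section to the SAP:

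1. **AE/SAE table.** Number and percentage of participants with any AE, any related AE and any SAE, with AEs also broken down by severity, overall and by first-stage arm (A1, A2), with exact 95% intervals. Count each participant once, at the worst severity.
2. **Outcome groups.** Simple counts or a listing, without intervals, because groups may be as small as four.
3. **Worsening.** From the ratings already tabulated, the number and percentage worse than baseline at the decision point and at the final visit. The study team should name the instrument and fix the margin before looking at the data. Do not add a count at any visit. Sections 1.3, 6.1.2 and 8.1 place the decision point differently (Day 14, three of five sessions, four of eight sessions, four weeks) and must be reconciled before this count can be defined.
4. **Section 8.2.** State that the exemption covers physical safety assessments only.

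The cost is one or two descriptive tables from data already collected. No visit, procedure or hypothesis test is added, and the sample size does not change.

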#### 9.4.4 BASELINE DESCRIPTIVE STATISTICS

Basic demographic tables will be generated for all characteristics at baseline, and then from baseline through follow-up periods. We will have general measures of central tendency for each variable (e.g., Mean, SD) measured categorically and continuously, and highlighted by measures of variability.

#### 9.4.5 PLANNED INTERIM ANALYSES

There are no statistical interim analyses planned that would determine the need to stop the study given the size of this pilot study.

#### 9.4.6 SUB-GROUP ANALYSES

There are not sub-group analyses planned as the focus of this pilot study is on Latinos living with HIV as a whole and only 10% of the clinic population is registered as female sex.

#### 9.4.7 TABULATION OF INDIVIDUAL PARTICIPANT DATA

For descriptive purposes, depression ratings will be tabulated over the course of the intervention for each participant and in aggregate.

#### 9.4.8 EXPLORATORY ANALYSES

There are currently not exploratory analyses that can be listed here given the pilot study was not powered to identify statistical significant relationship among the variables. Any exploratory analyses will be determined by the PI and research team.

### 10 SUPPORTING DOCUMENTATION AND OPERATIONAL CONSIDERATIONS

#### 10.1 REGULATORY, ETHICAL, AND STUDY OVERSIGHT CONSIDERATIONS

##### 10.1.1 INFORMED CONSENT PROCESS

A copy of the informed consent processes submitted to the IRB will be available upon request.

###### 10.1.1.1 CONSENT/ASSENT AND OTHER INFORMATIONAL DOCUMENTS PROVIDED TO PARTICIPANTS

Participants will always be given copies of the Human Subject Bill of Rights, the HIPAA authorization form, and the consent form, unless they verbally decline to accept them.

###### 10.1.1.2 CONSENT PROCEDURES AND DOCUMENTATION

All consenting procedures and discussions happen in-person and in a private room or office at the study site.

The informed consent process is informed by the UCSF IRB Consent Process and Documentation guidelines and Title 45-Code of Federal Regulations regarding human subject involvement in research. The obtainment of consent will be guided by a written document and an interactive, ongoing conversation between the PI, a research assistant, or Salud and Women's Clinic staff member and a participant. All documentation and conversations are readily available in English or Spanish.

The required eight elements of consent will be sectioned paragraph-by-paragraph in the informed consent document, which will be discussed in detail with a participant. At the start of the consent process, we will let the participant know that we prefer to have the consent form read out loud while they follow along. They will have the option to read the document by themselves, but we will strongly discourage this so as to ensure all elements of consent are fully acknowledged and comprehended.

As the consent process starts, each participant must acknowledge that they understand and agree to each section before continuing on to the next section (i.e., element of consent). At each section, we will ask a participant if they understand that they have the right to refuse to participate and that there are no consequences of doing so. We will inquire about their understanding of the study procedures (including the process of notifying their provider of their participation in the study), which include the possibility of multiple treatment reassessments, participation over a three-month follow-up period, and all risks that may result from participating.

---

#### 10.1.2 STUDY DISCONTINUATION AND CLOSURE

This study may be temporarily suspended or prematurely terminated if there is sufficient reasonable cause. Written notification, documenting the reason for study suspension or termination, will be provided by the suspending or terminating party to study participants, the study site, and the NIMH. If the study is prematurely terminated or suspended, [name] will promptly inform study participants, IRB, and the NIMH, and will provide the reason(s) for the termination or suspension. Study participants will be contacted, as applicable, and be informed of changes to study visit schedule.

Circumstances that may warrant termination or suspension include, but are not limited to:

- Determination of unexpected, significant, or unacceptable risk to participants;
- Demonstration of efficacy that would warrant stopping;
- Insufficient compliance of study staff to the protocol (ie, significant protocol violations);
- Data that are not sufficiently complete and/or evaluable;
- Determination that the primary endpoint has been met;
- Determination of futility;

The study may resume once concerns about safety, protocol compliance, and data quality are addressed, and satisfy the NIMH and UCSF IRB.

---

#### 10.1.3 CONFIDENTIALITY AND PRIVACY

Given the sensitivity of the study subject matter and possible disclosure of a psychiatric or HIV diagnosis, there is the potential to face consequences. This is primarily in having their participation disclosed - a study on depression for people living with HIV. There are no direct consequences associated with not participating, participating and dropping out of the study, or completing the study. There is the possible consequence of having others (e.g., family, friends, co-workers) find out about their participation. To guard against any potential consequences, we will collect our Certificate of Confidentiality (CoC) from the NIH. The CoC is available to all NIH-funded research, but can only be collected after IRB approval has been received.

The CoC information will also be specified on the consent form and described to each participant during the informed consent process. Only [name], the faculty mentor, and research staff will have access to a participant's contact information and raw data. All data that will be shared with the mentoring team will be de-identified. For participants in the trial, we will create a case file that is denoted by patient ID number that is generated at the time of the enrollment. All intervention paper files will be stored in an office space and locked inside a file drawer. All consent forms and tracking forms that have identifying information will be separated from all case files. All case files will be uploaded into a password protected file and stored on a UCSF secure server. All patient text-message conversations will be stored on encrypted study mobile phones before being downloaded into a password-protected and encrypted text or EML file and stored on UCSF's secure servers.

#### 10.1.4 FUTURE USE OF STORED SPECIMENS AND DATA

All data will be used for presentation and scientific conferences and peer-review publications. Aggregated data will be shared at monthly Salud Clinic meetings. No personal or identifying or singular data are ever presented.

#### 10.1.6 SAFETY OVERSIGHT

All safety risks will be regularly monitored during the study. [name] and his senior faculty mentor ([name]) will be in-person weekly during the study. [name] will also meet with [name]

(Internal Medical Monitor) bi-weekly during the same time period. Patient safety and data monitoring will be included as a meeting agenda item during individual meetings. The entire monitoring group will convene quarterly DSM meeting at the start of the study and up until the pilot study is completed.

#### 10.1.7 CLINICAL MONITORING

Clinical monitoring refers to independent monitoring plans. An agreement will be made with the PI and Drs. [name] and [name] (Clinic Director and Medical Director) to immediately report any detection of significant distress and breaches of confidentiality given that the study will take place at the Salud Clinic at ZSFGH. Should any breach of confidentiality or adverse events occur, the PI will convene an ad hoc meeting with Drs. [name] (faculty mentor) and [name] (internal medical monitor) to review options to stop the study, recommend removing the participant from the study, or change any intervention procedures to eliminate any potential risks that are occur at unacceptable levels.

#### 10.1.8 QUALITY ASSURANCE AND QUALITY CONTROL

The nature and sources of data/materials collected for this study are fully described in the Protection of Human Subjects Section that is available upon request and that was approved by the NIMH. Quality assurance measures following the E6 Good Clinical Practice Guidance 1.46 will guide all research activities for this study. This will include weekly meetings with [name] senior faculty mentor to review each individual case and formally documented written reports of participant activity. Further, together, they will oversee the annual all-mentoring team meeting to outline progress and benchmarks of the research activities and to discuss and address any barriers and challenges to the progress of the research activities. The frequency of meetings between the PI and faculty mentor, along with co-mentors and scientific advisors, will ensure that the study progresses in accordance with the timeline outlined. Any significant delays for any study activities will be reported to the NIMH program officer.

#### 10.1.9 DATA HANDLING AND RECORD KEEPING

##### 10.1.9.1 DATA COLLECTION AND MANAGEMENT RESPONSIBILITIES

Data collection will be the responsibility of the research staff and [name] who directly supervises them. The investigator will be responsible for ensuring the accuracy, completeness, legibility, and timeliness of the data reported.

All source documents will be completed in a neat, legible manner to ensure accurate interpretation of data.

Hardcopies of the study visit worksheets will be provided for use as source document worksheets for recording data for each participant consented/enrolled in the study.

The data systems used in this study are directly sourced from the UCSF IT Systems and includes password protection and internal quality checks, such as automatic range checks, to identify data that appear inconsistent, incomplete, or inaccurate. Clinical data will be entered directly from the source documents.

